### ***Antimicrobial Resistance (AMR) Monitoring Outcomes***

*AMR primary outcome 1:* Prevalence of genetic determinants of resistance to macrolides including those determinants known to be found in *Streptococcus pneumoniae*, *Streptococcus pyogenes*, and *Staphylococcus aureus* from nasopharyngeal swabs in children 1-59 months old at 24 months from baseline. We anticipate inclusion of 50 communities per arm (150 total)

provides at least 80% power to detect an absolute difference of 8% in all age groups between any two arms, assuming:

- Baseline resistance of 30% (from MORDOR I)
- ICC of 0.045 (from multiple studies)
- 30 specimens from each of 50 communities from each arm
- Alpha of 0.05/2

*AMR primary outcome 2:* Load of genetic determinants of resistance to macrolides including those determinants known to be found in *Campylobacter*, *Salmonella* spp., *Shigella* spp., and *Escherichia coli* from rectal swabs in children 1-59 months old at 24 months from baseline. We anticipate inclusion of 50 communities per arm (150 total) provides approximately 80% power to detect a 1.4-fold difference in proportion of bacterial reads that are resistant all age groups between any two arms, assuming:

- SD of resistance load (on log scale) equal to 3.1 (MORDOR I)
- ICC of 0.02 (MORDOR I)
- 30 specimens from each of 50 communities from each arm
- Alpha of 0.05/2

*AMR secondary outcome (as an example of detectable effects for other AMR secondary outcomes):* For proportion of pneumococcal isolates from nasopharyngeal swabs in children 1-59 months resistant to macrolides on phenotypic testing, we anticipate inclusion of 50 communities per arm (150 total) provides approximately 80% power to detect a 8% absolute increase between any two arms, assuming:

- Baseline resistance of 10% (from MORDOR I)
- ICC of 0.045 (from multiple studies)
- 10 specimens from each of 20 communities from each arm (8 after accounting for specimen nongrowth)
- Alpha of 0.05

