The overall objectives of trial are to determine the optimal age group to treat with biannual oral azithromycin distribution to reduce child mortality and to compare selection for antimicrobial resistance across different age-based strategies for azithromycin distribution. In a series of secondary outcomes and parallel studies, the trial will also evaluate large-scale implementation. We propose the following specific aims for the Mortality/Resistance trial:

Specific Aim 1.

1a. To compare efficacy of biannual oral azithromycin distribution to reduce mortality in children 1–59 months old in communities distributing azithromycin to ages 1–59 months (azithro 1–59) compared to placebo. *We hypothesize that the community-level mortality rate in children 1–59 months old at 2.5 years from the first enrollment will be lower in the azithromycin arm.*

1b. To compare efficacy of biannual oral azithromycin distribution to reduce mortality in children 1–11 months old in communities distributing azithromycin to ages 1–11 months (azithro 1–11) compared to placebo. *We hypothesize that the community-level mortality rate in children 1–11 months old at 2.5 years from the first enrollment will be lower in the azithromycin arm.*

1c. To compare efficacy of biannual oral azithromycin distribution to reduce mortality in children 12–59 months old in communities distributing azithromycin to ages 1–11 months (azithro 1–11) compared to 1–59 months (azithro 1–59). *We hypothesize that the community-level mortality rate in children 12–59 months old at 2.5 years from the first enrollment will be lower in the azithro 1–59 arm.*

Specific Aim 2.

2a. To compare the community-level prevalence of genetic determinants of macrolide resistance in nasopharyngeal samples from children 1–59 months old in programs targeting azithromycin to 1–11 months, 1–59 months, or providing placebo. *We hypothesize that the community-level prevalence of resistance determinants after 2 years of distributions will differ in these 3 arms. Specifically, we hypothesize that the community-level prevalence of resistance determinants will be greater in the azithromycin arms than the placebo arm. In addition, we hypothesize that the prevalence of resistance will be greater in the azithro 1–59 arm than the azithro 1–11 arm.*

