4.4.8.3. Measurement of Sample Based Outcomes

In the Mortality and Resistance Trial, 150 AMR communities from the Dosso region will be randomly selected from the pool of eligible communities and followed to monitor antimicrobial resistance. Samples will be collected in a random subset of communities at baseline and in all 150 AMR communities after 2 years of distributions. For primary outcomes, samples will be processed from a subset of 150 communities.

In each of the selected Mortality/Resistance Trial communities, 30 children aged 1–59 months,

30 children aged 7–12 years, and 30 caregivers/guardians of eligible children will be randomly selected for additional monitoring. Nasopharyngeal samples will be collected from all sampled individuals. From children aged 1–59 months, rectal swabs, RDT, and dried blood spots will also be collected. In the sample of children aged 1–59 months, 10 children will be randomly selected for an additional nasopharyngeal swab which will be used for phenotypic testing. Samples will be collected at baseline and after 2 years of distributions.

To randomly select individuals for population-based monitoring in the Mortality/Resistance Trial, census data will be used. In the 150 Dosso communities selected for additional monitoring, the baseline and 24-month census will be separate from treatment and will include data collection on children aged 7–12 years old. The random samples of children in both age groups and caregivers/guardians will be selected from the census. To ensure that samples are collected on 30 individuals in each group, 50 children in both age groups and 50 caregivers/guardians will be randomly selected from the census data.

60 previously untreated communities will be incorporated into the Mortality/Resistance Trial in Round 4 and will receive rectal swab baseline collections. This is to account for rectal swab baseline samples collected in Round 1 that were damaged and unusable. 1 rectal swab will be collected from 30 children aged 1–59 months per community. Samples from community latrines and chicken feces will also be collected when available from the homes of the 30 children selected for this sample collection.

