## 3.3. Statistical Principles

### 3.3.1. Confidence intervals and *P*-values

The primary analysis for the mortality trial is prespecified to occur at alpha of 0.05, as follows. We propose to use a fixed-sequence, hierarchical testing approach for the three mortality primary outcomes [4]:

The staged testing approach will maximize the trial's power. Our rationale for a fixed-sequence testing approach is if there is no benefit of treating all children 1-59 mo compared with

placebo, then the trial would be unlikely to demonstrate benefit between treatment in the narrower age subgroups. Note that the hypothesis testing in the mortality trial and implementation trial will proceed independently for primary outcomes along the same sequence of tests. Regardless of the hypothesis testing results, we will report 95% confidence intervals around estimates of the incidence rate ratio for the comparisons of the trial arms.

In the mortality trial AMR substudy, we propose a second set of tests. There are two primary outcomes measured among children 1-59 months: prevalence of macrolide resistance measured in NP swabs, and load of genetic determinants of macrolide resistance measured in rectal swabs. Each primary outcome in the substudy will be examined separately at alpha of 0.05. For each outcome, we propose three pair-wise comparisons between the study groups (Placebo v 1-59mo, Placebo v 1-11mo, 1-59mo v 1-11mo). We will compute *P*-values using a permutation test with a step-down minP approach to account for multiple testing [5,6]. Additional secondary comparisons between groups in the substudy will include prevalence of genetic determinants of resistance to non-macrolide antibiotics (NP swabs) and load of genetic determinants to non-macrolide antibiotics (rectal swabs). Within each outcome, we will report *P*-values adjusted to control the false discovery rate at 5% the Benjamini-Hochberg approach [7]. For all AMR endpoints, we will additionally report unadjusted *P*-values, which will be less conservative to detect undesirable outcomes resulting from mass distribution of azithromycin.

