9	2021-04-06	
 
Added MORDOR continuation substudies to the outcomes definitions in section 6.1
 
Updated the multiple testing procedure planned for AMR substudy in section 4.1
 
Clarified the ITT analysis will only include enrolled grappes
 

10	2022-02-04	
 
Added sensitivity analyses to Delivery Trial treatment coverage outcome in section 6.2
 

11	2022-05-24	
 
• Updated the format to include 3 different sections for the 3 different trials.
 
• Added in the Programmatic Trial section.
 

12	2022-05-27	
 
• Removed details of CSI clinic visit outcome measurement and analyses until those details can be confirmed vis-à-vis field measurement and logistics.
 

13	2022-10-21	
 
• Updated wording of person-time calculations for Mortality trial
 

14	2023-07-24	
 
• Included in the trial overview details of study team masking (membership, timing, rationale), section 2.
 
• Updated Figure 1 and included footnote
 
• Updated the language of tempering roots from 1/3 or 1/4 to 1/4 or 1/6 or 1/8, section 3.2.2.
 
• Removed redundant paragraph for masking in the section of interim Analysis, section 3.2.5
 
• Clarified the timing of the primary analysis, to be exactly 2 years after completion of enrollment, section 3.2.6
 
• Revised Mortality trial primary analysis to align notation with the final adaptive randomization schedule, including the model specification and permutation test, section 3.5.2
 
• Moved Delivery Trial and Programmatic Trial analysis plans to separate SAPs to make the SAP easier to navigate.
 

15	2023-10-17	
 
• Updated Figure 1 to reflect the final count of communities screened and enrolled in the programmatic trial.
 

16	2024-09-25	
 
• Updated AMR sample size and power calculations. The lab is going to be processing all 150 communities for the AMR outcomes, so we can include the full 150 communities in the primary AMR analyses, as opposed to the 60 that we listed originally.
 

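### SAP 3.2.3: the phenotypic-resistance example claims about 80% power with 50 communities per arm but lists 20 as its input (about 44%); the alpha behind the two AMR primaries also differs from the planned test

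*SAP*

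**What the plan says.** **Phenotypic example (SAP 3.2.3, Antimicrobial Resistance Monitoring Outcomes).** The SAP offers this calculation as an illustration for the other AMR secondary outcomes. The claim is: "we anticipate inclusion of 50 communities per arm (150 total) provides approximately 80% power to detect a 8% absolute increase between any two arms". The assumptions are baseline resistance 10%, ICC 0.045, alpha 0.05, and "10 specimens from each of 20 communities from each arm (8 after accounting for specimen nongrowth".

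**Where the two community counts come from.** The version 16 entry in the SAP revision history says that the laboratory will process all 150 communities, "so we can include the full 150 communities in the primary AMR analyses, as opposed to the 60 that we listed originally". Protocol 4.4.8.3 says that in each selected community "10 children will be randomly selected for an additional nasopharyngeal swab which will be used for phenotypic testing", and that samples are collected "in all 150 AMR communities after 2 years of distributions".

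**AMR primaries.** For nasopharyngeal prevalence, SAP 3.2.3 says that 50 communities per arm "provides at least 80% power to detect an absolute difference of 8% in all age groups between any two arms", assuming 30% baseline, ICC 0.045, 30 specimens per community and an alpha of 0.05/2. The rectal-load primary uses the same alpha. SAP 3.3.1 plans something else: "Each primary outcome in the substudy will be examined separately at alpha of 0.05", with three pairwise comparisons per outcome and permutation P-values by step-down minP. SAP 3.5.2 repeats that procedure. Protocol Section 3, Aim 2a, gives the expected direction: "we hypothesize that the community-level prevalence of resistance determinants will be greater in the azithromycin arms than the placebo arm".

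**The concern.** The phenotypic example prints two different numbers of communities per arm within one item, and power depends heavily on which is used. A reader who rebuilds the calculation from the listed assumptions gets little more than half the stated power. Because the example stands in for other AMR secondary outcomes, the wrong input could be carried into a judgement of what those outcomes can detect.

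For the two primaries, the power section divides alpha by two, but nothing in the analysis sections does. The two outcomes are not split, and the comparisons within each number three, not two. The stated power therefore belongs to a procedure that the plan does not use.

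**Working it through.** **Method.** Effective sample size per arm is n_eff = k·m / [1 + (m − 1)·ICC], for k communities and m specimens each. Power is Φ(d/SE − z), with SE = √{[p1(1−p1) + p2(1−p2)] / n_eff} (unpooled). Tests are taken as two-sided. SAP 3.2.4 says this for the mortality hypothesis; for AMR it is an assumption.

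**1. Phenotypic example, 10% against 18%.** Inputs from SAP 3.2.3: m = 8 usable specimens, ICC 0.045, alpha 0.05 (z = 1.960).

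- Design effect: 1 + 7 × 0.045 = 1.315.
- Variance term: 0.10 × 0.90 + 0.18 × 0.82 = 0.2376.

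The plan's own figure, with k = 50:
- n_eff = 400/1.315 = 304.2; SE = √(0.2376/304.2) = 0.0279.
- 0.08/0.0279 = 2.86, and Φ(2.86 − 1.96) = **0.82** (0.81 with pooled variance).
- Detectable with 80% power: about **7.8 points**. The stated 80% and 8 points are reproduced.

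The listed input, with k = 20:
- n_eff = 160/1.315 = 121.7; SE = √(0.2376/121.7) = 0.0442.
- 0.08/0.0442 = 1.81, and Φ(1.81 − 1.96) = **0.44** (0.435 pooled).
- Detectable with 80% power: about **13 points**.

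More generous readings of the 20-community line:

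| Specimens per community | Test | Power, 20 communities |
|---|---|---|
| 8 | two-sided 0.05 | 44% |
| 8 | one-sided 0.05 | 57% |
| 10 | two-sided 0.05 | 50% |
| 10 | one-sided 0.05 | 62% |

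None reaches 80%. At 8 specimens and two-sided 0.05, 48 communities per arm are needed (49 with pooled variance). The listed 20 equals 60/3, the per-arm count under the plan that version 16 replaced.

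**2. Nasopharyngeal primary, 30% against 38%.** Inputs: k = 50, m = 30, ICC 0.045.

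- Design effect: 1 + 29 × 0.045 = 2.305; n_eff = 1500/2.305 = 650.8.
- SE = √[(0.21 + 0.2356)/650.8] = 0.0262; 0.08/0.0262 = 3.06.
- At alpha 0.025 (z = 2.241): Φ(3.06 − 2.24) = **0.79**. Detectable with 80% power: about **8.1 points**.
- At alpha 0.05: power 0.86, detectable 7.3 points. The stated 8 points thus fits a true 0.025 level, not 0.05/2 as shorthand for the two tails of a 0.05 test. The phenotypic item in the same list also prints plain 0.05.
- For a fall to 22% at alpha 0.025: SE = √[(0.21 + 0.1716)/650.8] = 0.0242, and power = 0.86.

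Under the planned three-comparison procedure, the first-step critical value is about 2.345 (normal approximation by simulation). On that step alone, power is Φ(3.06 − 2.345) = 0.76. The full step-down gives about 0.77 to 0.79, depending on where the third arm lies, which the documents do not specify.

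**The case against.** **The headline is right, so this is only a stale line.** Largely true. The sentence that most readers will use says 50 communities, and 50 reproduces the claim. The 44% belongs to the listed input alone. A reader might infer that the phenotypic comparison is really powered at 44%. The documents do not support that: the protocol takes the phenotypic swab in the selected AMR communities and samples all 150 at two years.

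**Twenty could be deliberate.** Version 16 draws its conclusion for the primary AMR analyses, and the phenotypic outcome is secondary. The protocol says where the swabs are taken, not from how many communities they are cultured. This part stands, and it is why the number should be confirmed before the line is edited. It does not save the passage: if 20 is right, the 50 and the 80% above it are wrong.

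**Both counts come from a version change.** A difference between a change log and current text is no error. Here, though, both numbers are in the current text of one item. The log only suggests how the mismatch arose.

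**A fixed per-comparison alpha is ordinary shorthand for minP.** Also largely true. At 0.025 the nasopharyngeal power is within about 3 points of the step-down result, and the shortfall from 80% is under one point. The SAP words that effect as an unsigned difference, and a decrease clears 80%. The step-down figures rest on an assumed third-arm position and two-sidedness, so they should not be written into the SAP as they stand. What remains is a mismatch in the stated procedure and an at-least claim that just fails in the direction of Aim 2a.

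**Conclusion.** The phenotypic item contradicts itself. Of its two community counts, only 50 per arm supports the stated power: about 82%, against about 44% with 20. This assumes 8 usable specimens, ICC 0.045 and a two-sided 0.05 test; no variant tried with 20 communities exceeded 62%. It is a minor error of a stated input, and confidence in it is high.

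The alpha mismatch for the AMR primaries is real but smaller. Nasopharyngeal power for 30% against 38% is 79% at 0.025, which is approximately but not at least 80%; 80% needs about 8.1 points. A reader might infer that the primaries are materially underpowered, and the figures do not show that.

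A reader might also infer that the 1.4-fold rectal-load claim is wrong, because the SD of 3.1 on a log scale is given without a base. No error is shown. With ICC 0.02, n_eff = 1500/1.58 = 949.4, SE = 3.1 × √(2/949.4) = 0.142, and the 80% detectable difference at alpha 0.025 is 3.083 × 0.1423 = 0.439 log units. If the base is 2, that is 1.36-fold, which rounds to 1.4. The missing base is an omitted label and is not part of this finding.

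**What to change.** 1. Confirm with the laboratory how many communities' phenotypic swabs are cultured.
   - If all 150: change the input line in SAP 3.2.3 from 20 to 50 communities per arm. The 80% and 8 points stay.
   - If only 60: restate the headline as 20 per arm, with about 44% power for 8 points, or 80% power for about 13 points.
2. For both AMR primaries, replace the alpha of 0.05/2 with the procedure in SAP 3.3.1 and 3.5.2 (0.05 per outcome, three pairwise comparisons, step-down minP), and state whether the tests are two-sided. If 0.025 is kept as a planning approximation, say so.
3. For the nasopharyngeal outcome, write approximately 80% in place of at least 80%.

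The cost is one enquiry, a few words in the SAP and a check against the companion power notebook. Sampling, trial conduct and the planned tests are untouched.

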### 3.2.4. Statistical framework

The overall analysis is divided into two aspects: 1) A single frequentist analysis, conducted at the time 2.5 years after enrollment, will test the hypothesis that azithromycin MDA reduces childhood mortality. The hypothesis tests will be superiority tests (as opposed to equivalence or noninferiority analyses) and will be two-sided. 2) Ongoing analyses beyond the primary endpoint, reflecting the perpetual nature of the trial, will be conducted using a Bayesian perspective.

### 3.2.5. Statistical interim analyses and stopping guidance

The adaptive design will naturally change allocation, evolving toward higher allocation probabilities for arms most likely to have lowest mortality. From a frequentist perspective, we propose a interim analysis at 18 months after the first enrollment (12 months of data in each community). The analysis will be based on the Haybittle-Peto boundary which results in an interim alpha of 0.001. The alpha of the final analysis will continue to be 0.05 according to the rule.[3] The Data and Safety Monitoring Committee will be notified of the results, and if the p-value (hierarchical approach, same as primary outcome) is <0.001, then the DSMC and if appropriate, one or more PIs will meet to decide a course of action. Factors in any decision would include interest in both the 1-59 month and 1-11 month MDAs, and AMR. Early

discontinuation for other reasons (political, ethical, lack of resources, etc) would mandate final frequentist analysis at alpha of the full final prespecified value based on all available data (incorporating any alpha spending, as needed). We note that the DSMC may advise discontinuation based on evidence of harm, even in the absence of statistical significance. Bayesian inferences are unchanged by the application of interim analyses. Continuous Bayesian monitoring will be conducted.

### Interim reporting

Reports will be planned for the Data and Safety Monitoring Committee. We will report the number of treatments delivered, the number of communities enrolled at each phase, and the coverage by community (i.e., process indicators). Overall mortality rates by age group (1-11, 12-59, and 1-59) will be tabulated overall in open reports.

We note that response adaptive randomization for the mortality trial will begin for communities enrolled at and after the one year mark.

### 3.2.6. Timing of the primary analysis

Mortality. The primary analysis will occur 2 years (rounded to the day) after the completion of enrollment. The analysis will use all the data available at that time; i.e., we do not propose to wait until phase completion for individuals enrolled and being currently followed at the 2-year mark, but rather, to use all complete data records at that moment.

AMR. Analysis of resistance outcomes will occur after the 24-month community-based samples are analyzed in the lab.

[figure not shown]
### 3.2.7. Timing of outcome assessments

Mortality outcomes are measured at the end of each prespecified inter-census interval, intended to be six months in duration. The primary analysis will include outcomes assessed up to 2.5 years after the first enrollment. AMR outcomes are assessed at baseline and after 24 months of intervention.

## 3.3. Statistical Principles

### 3.3.1. Confidence intervals and *P*-values

The primary analysis for the mortality trial is prespecified to occur at alpha of 0.05, as follows. We propose to use a fixed-sequence, hierarchical testing approach for the three mortality primary outcomes [4]:

The staged testing approach will maximize the trial's power. Our rationale for a fixed-sequence testing approach is if there is no benefit of treating all children 1-59 mo compared with

placebo, then the trial would be unlikely to demonstrate benefit between treatment in the narrower age subgroups. Note that the hypothesis testing in the mortality trial and implementation trial will proceed independently for primary outcomes along the same sequence of tests. Regardless of the hypothesis testing results, we will report 95% confidence intervals around estimates of the incidence rate ratio for the comparisons of the trial arms.

In the mortality trial AMR substudy, we propose a second set of tests. There are two primary outcomes measured among children 1-59 months: prevalence of macrolide resistance measured in NP swabs, and load of genetic determinants of macrolide resistance measured in rectal swabs. Each primary outcome in the substudy will be examined separately at alpha of 0.05. For each outcome, we propose three pair-wise comparisons between the study groups (Placebo v 1-59mo, Placebo v 1-11mo, 1-59mo v 1-11mo). We will compute *P*-values using a permutation test with a step-down minP approach to account for multiple testing [5,6]. Additional secondary comparisons between groups in the substudy will include prevalence of genetic determinants of resistance to non-macrolide antibiotics (NP swabs) and load of genetic determinants to non-macrolide antibiotics (rectal swabs). Within each outcome, we will report *P*-values adjusted to control the false discovery rate at 5% the Benjamini-Hochberg approach [7]. For all AMR endpoints, we will additionally report unadjusted *P*-values, which will be less conservative to detect undesirable outcomes resulting from mass distribution of azithromycin.

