### Antimicrobial Resistance Substudy

The primary analysis for resistance outcomes from nasopharyngeal swabs will be ANOVA to compare the community-level proportion of individuals with any macrolide resistant genetic determinants across the three arms. The primary analysis for rectal swabs will be ANOVA to compare community-level mean load of macrolide resistant genetic determinants across the three arms. For both sets of swabs, secondary analyses examining resistance in other classes of antibiotics and other age groups will be conducted similarly.  $P$ -values for all resistance analyses will be computed using a permutation test, using a step down minP procedure to control for three pairwise comparisons in each primary outcome, and using a Benjamini-Hochberg correction to control the false discovery rate across additional (non-macrolide) endpoints, described above in section 4.1.

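### The step-down minP for the three resistance comparisons is valid but, read as the ordinary procedure, needlessly strict after the first rejection, costing 0 to about 7 points of power depending on the scenario

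*SAP*

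**What the plan says.** SAP 3.3.1 names two primary outcomes in the resistance substudy, prevalence of macrolide resistance determinants in nasopharyngeal swabs and their load in rectal swabs. It states: "Each primary outcome in the substudy will be examined separately at alpha of 0.05". Within each outcome there are three pairwise comparisons (placebo v 1–59, placebo v 1–11, 1–59 v 1–11), with P-values from a "permutation test with a step-down minP approach to account for multiple testing". SAP 3.5.2 (Antimicrobial Resistance Substudy) repeats the rule, "using a step down minP procedure to control for three pairwise comparisons in each primary outcome", and calls the primary analysis an ANOVA across the three arms. Neither section says that logical relations between the three hypotheses will be used. SAP 3.3.1 also promises unadjusted P-values for every resistance endpoint, as a less conservative look for undesirable effects.

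The power statement in SAP 3.2.3 for nasopharyngeal prevalence is that 50 communities per arm "provides at least 80% power to detect an absolute difference of 8% in all age groups between any two arms", with "Baseline resistance of 30% (from MORDOR I"), "ICC of 0.045 (from multiple studies"), 30 specimens per community and "Alpha of 0.05/2". Protocol Section 3 (Specific Aim 2a) hypothesises more resistance in both azithromycin arms than in placebo, and more in azithro 1–59 than in azithro 1–11.

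**The concern.** An ordinary step-down minP judges the smallest P-value against the minimum over three hypotheses, the next against the minimum over two, and the last alone. With three arms the middle step guards against a configuration that cannot occur. If arms A and B differ, then A = C and B = C cannot both be true. At most one true null is left, so the remaining pairs can each be tested at the full 0.05 without the family-wise error exceeding 5% (closed testing; Shaffer's refinement).

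What is at stake is power on the comparisons decided at the second step. Under the protocol's hypothesised ordering, placebo v azithro 1–59 is usually the largest contrast and is rejected first, so the comparisons involving azithro 1–11 tend to fall to the second step. They address the trial's reason for the infant-only arm, namely whether narrower treatment limits selection for resistance.

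**Working it through.** **Inputs.** SAP 3.2.3: 50 communities × 30 specimens per arm, ICC 0.045, 30% baseline, 8-point difference. Protocol 4.4.1: resistance communities allocated 1:1:1. Two-sided testing is assumed; SAP 3.2.4 ("noninferiority analyses) and will be two-sided") says so for the mortality hypothesis.

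**The plan's own figure.** Design effect = 1 + 29 × 0.045 = 2.305. Effective sample per arm = 1500 / 2.305 = 650.8. With p = 0.34 (mean of 0.30 and 0.38), the standard error of a difference is √(2 × 0.34 × 0.66 × 2.305 / 1500) = 0.02626, so the expected z is 0.08 / 0.02626 = 3.05. At two-sided alpha 0.05/2 (cut-off 2.24) power is 79.0%, or 79.3% with unpooled variance. The stated figure of at least 80% is reproduced to within about a point.

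**The two procedures.** Normal approximation, three independent arm means with variance 0.34 × 0.66 × 2.305 / 1500, 2,000,000 draws per scenario.
- Free step-down: |z| cut-offs 2.34 (largest of three pairs), then 2.21 (larger of two pairs sharing an arm), then 1.96.
- Constrained: the largest |z| must exceed 2.34; every other pair is then judged against 1.96.

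Power in %, free → constrained; arms ordered placebo / 1–11 / 1–59:

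| True prevalence | Placebo v 1–11 | Placebo v 1–59 | 1–11 v 1–59 | At least one rejection (both procedures) |
|---|---|---|---|---|
| 30/30/38 | null pair | 78.5 → 82.2 | 78.5 → 82.2 | 88.6 |
| 30/38/38 | 78.5 → 82.2 | 78.5 → 82.2 | null pair | 88.6 |
| 30/32/38 | 8.5 → 11.6 | 77.1 → 78.9 | 52.3 → 59.2 | 81.3 |
| 30/34/38 | 25.3 → 31.6 | 76.5 → 77.4 | 25.2 → 31.6 | 78.3 |
| 30/36/38 | 52.3 → 59.2 | 77.1 → 78.9 | 8.5 → 11.5 | 81.3 |
| 30/38/46 | 85.7 → 86.1 | 100 → 100 | 85.7 → 86.1 | 100 |

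In 30/30/38, rejecting both true pairs rises from 68.4% to 75.8%.

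**Error control.** Under 30/30/30 the family-wise error is 5.0% for both procedures. With one true null pair (30/30/38) it is 3.6% for the free version and 4.9% for the constrained one. In this approximation no draw lost a rejection under the constrained rule.

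**Check with real permutation tests.** Beta-binomial community data, 999 permutations, 2,500 replicates per scenario. In 30/30/38, 30/38/38 and 30/34/38, and on 1–11 v 1–59 in 30/32/38, the gain on the affected pairs was 2.5 to 5.7 points when the three-arm step used a studentised statistic, and 3.5 to 9.0 with raw mean differences. In 30/38/46 the studentised version gave +0.6 and −1.2 on the adjacent pairs, because the two-arm permutation uses a different variance reference from the three-arm one. Raw differences gave +5.5 and +4.1 there. The SAP does not say which statistic is permuted.

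**ANOVA as the first step.** With the middle arm exactly halfway, the between-arm sum of squares in standard-error units equals z² for the extreme pair. The global test then needs |z| > √5.991 = 2.45, against 2.34 for minimum P. In the simulation an ANOVA gate dropped at least one rejection the current plan would make in 0.6% (30/30/38), 1.0% (30/32/38) and 1.3% (30/34/38) of trials.

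**The case against.** The strongest reply is that nothing here is wrong: the planned procedure holds the family-wise error at 5%, and the chance of finding at least one difference is the same either way. That stands; this is a missed efficiency.

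Second, the promised unadjusted P-values let a reader come close to the constrained result, since it is the larger of the global minimum P and the unadjusted pairwise P. That softens the loss, but a supplementary P-value is not a confirmatory one, and the two-arm permutation would still be unspecified.

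Third, the power calculation used alpha 0.05/2 (cut-off 2.24), close to the second-step cut-off of 2.21, so the planned 80% already roughly pays for the adjustment. True. There is no shortfall against the stated design, only power that could be had at no cost in error.

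Fourth, the SAP never excludes a constrained step-down. Also true: the free version is the natural reading of its silence, not its words.

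Fifth, the revision history shows this multiplicity rule updated in April 2021 and the current SAP dated September 2024. Relaxing it this late could look opportunistic. That is a reason to date the change clearly and make it before resistance results by arm are seen.

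**Conclusion.** The point holds as an avoidable inefficiency. On the nasopharyngeal inputs, the free step-down gives up 0 to about 7 points of power. The loss is largest on comparisons involving azithro 1–11 when that arm lies between the other two within an 8-point range. It is about 3.7 points per true pair when two arms are equal, 1 to 2 points on placebo v 1–59 in the ordered scenarios, and under 0.5 point with equal 8-point steps. These sizes rest on the normal approximation, two-sided tests and the free-step-down reading.

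Three stronger readings are not supported. A reader might infer that error control fails; it does not. A reader might take 4 to 7 points as the loss on all the primary resistance comparisons; it applies only to those decided at the second step, and even after the gain some, such as 25% to 32% in 30/34/38, remain poorly powered. A reader might carry the figures over to rectal load at the stated 1.4-fold effect; the SAP gives the SD on a log scale without its base, so no figure can be given there.

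**What to change.** In SAP 3.3.1 and 3.5.2, state the following for each primary resistance outcome.
- Step 1: a permutation test of the minimum P over all three pairs, at 0.05.
- Step 2, if it rejects: the two remaining pairs are each tested at unadjusted 0.05, permuting labels only between the two arms compared.
- Each adjusted P-value is the larger of the global minimum-P value and the pairwise P-value.

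Do not make the ANOVA the gate, since it can lose rejections that the current plan would make. Name the permuted statistic in the same edit.

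The cost is a sentence or two in each section and a few lines of code, with no new data and family-wise error still at or below 5%. The change should be dated and adopted before resistance results by arm are seen.
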